### 6 COHORT DEFINITION

Participants for this trial will be recruited from among former HVTN 704/HPTN 085 (NCT02716675) study participants who met criteria for transition to Schedule 2 or Schedule 3 in that study and who meet the inclusion/exclusion criteria that are specified in protocol section 5.

### 7 RANDOMIZATION

This study is not randomized. Outcomes will be compared using randomized treatment assignment from HVTN 704/HPTN 085.

### 8 BLINDING

Although this study is not randomized, and study product is not administered, precautions have been taken to protect the integrity of the ongoing HVTN 704/HPTN 085 study.

Participants eligible for screening and enrollment into this study are a subset of all HVTN 704/HPTN 085 HIV-infected participants. Participant recruitment lists are restricted to study staff who already have knowledge of HVTN 704/HPTN 085 HIV-infected participants (details in the HVTN 804/HPTN 095 SSP). HVTN 704/HPTN 085 participant identifiers were masked in this study's database until HVTN 704/HPTN 085 was fully completed and unblinded. Unlike other HVTN studies in which enrollment data is available to all HVTN members, enrollment data for this study are restricted to study team members.

### 9 SAMPLE SIZE

We calculate the expected trial sized under different scenarios for the percentage of enrolled participants out of the total number of endpoint infected cases from HVTN 704/HPTN 085; scenarios include 25%, 50%, and 75%. Eligible placebo recipients will be capped such that the overall placebo to VRC01 recipient ratio of enrolled participants is at most approximately 1:1. Given that the parent HVTN 704/HPTN 085 study was randomized at a 1:2 placebo to VRC01 ratio, we would only expect to cap the number of eligible placebo recipients if prevention efficacy (PE) exceeds 50%. Given this constraint, along with an assumption of a common prevention efficacy at each dose (PE10 and PE30), the expected trial size will depend on different levels of PE. Under the null hypothesis (PE10 = PE30 = 0%), the total expected number of endpoint infections among placebo recipients is 26 and VRC01 recipients is 55 (Table 4-3 in the parent protocol HVTN 704/HPTN 085); therefore, we assume a trial size of 7, 13 or 20 placebo recipients and 14, 28, or 41 VRC01 recipients depending on the enrollment ratio. Under the alternative hypothesis (PE10 = PE30 = 60%), the total expected number of endpoint infections among placebo recipients is 37 and VRC01 recipients is 30 (Table 4-3 in the parent protocol); therefore, under the different enrollment ratio scenarios, we assume a trial size of 8, 15, or 23 placebo recipients and an equal number of VRC01 recipients so as not to exceed a 1:1 ratio. These six sample size scenarios represent estimated upper and lower bounds for sample size

given the expected number of endpoint infections under the null and alternative hypotheses respectively, as well as various scenarios for the percentage of eligible participants who will ultimately enroll in HVTN 804/HPTN 095.

### Sample size considerations for time to ART re-initiation criteria (primary objective 1)

Using data from the placebo arm of a therapeutic vaccine study which enrolled early treated patients (80), we modeled the time T (in weeks) to meet re-initiation criteria as a Weibull distribution with survival function  $P(T > t) = \exp[-(\lambda t)p]$ , where  $\lambda = \exp(-2.932) = 0.053$  and p = 2.014. From these parameters, we estimated the median time to meet re-initiation criteria as 15.6 weeks in the AMP placebo recipients. We can express the treatment effect in terms of either the hazard ratio  $\theta$  or the factor  $\beta$  by which treatment increases the median time to meet re-initiation criteria;  $\beta$  and  $\theta$  are related by  $\beta = \theta - 1/p$ .

We model censoring of time to re-initiation criteria using an exponential model and a maximum follow-up time of 72 weeks, where follow-up is censored at a rate of 20% per year due to either study termination or re-initiation of ART before reaching the re-initiation criteria. Simulating 10,000 trials based on these models of time to re-initiation criteria and censoring, we computed power using a log rank test with alpha equal to 0.05. Power for a 40%, 50%, 60%, and 70% reduction in hazard under different enrollment rate and prevention efficacy scenarios are shown in Table 4-1. These hazard reductions correspond to 29%, 41%, 58%, and 82% increases in the median time to meet re-initiation criteria. Therefore, if VRC01 increases the median time to re-initiation criteria 58% and the enrollment rate is 50%, then under the parent study null hypothesis power to detect a difference in time to re-initiation criteria is 72% while under the alternative hypothesis power is 62%.

Table 4-1 Power under different prevention efficacy results, different enrollment rates and different treatment effects, expressed as either reduction in hazard or percent increase in median time to meet re-initiation criteria

		Null hypothesis			Alternative hypothesis		
	25%	50%	75%	25%	50%	75%	
Expected	number of placebos	7	13	20	8	15	23
Expecte	d number of VRC01	14	28	41	8	15	23
Reduction in hazard	% Increase in median time to meet re-initiation criteria				GC	5	75
40%	29%	20%	32%	44%	16%	26%	37%
50%	41%	31%	50%	67%	24%	42%	58%
60% 58%		46%	72%	89%	36%	62%	81%
70%	82%	65%	91%	98%	54%	83%	96%

### Sample size considerations for safety (primary objective 2)

The goal of the safety evaluation for this study is to identify safety concerns associated with ATI. The ability of the study to detect serious adverse events (SAEs) (see protocol Section 4.2.4.1) can be expressed by the true event rate above which at least 1 SAE would likely be observed and the true event rate below which no events would likely be observed. Under the enrollment rate and PE scenarios described in protocol Section 4.1, Table 4-2 shows the true event rate such that there is a 90% chance of observing at least 1 event (or no events) among three groups; 1) the placebo recipients only, 2) the VRC01 recipients only, or 3) all enrolled participants.

Table 4-2 True event rates above which at least 1 SAE (or below which no events) would likely be observed in a group of size n participants. Event rates are computed separately for various values of n given by the range and midpoint for the estimated number of participants among 3 groups; 1) the placebo recipients only, 2) the VRC01 recipients only, or 3) all enrolled participant based on the enrollment scenarios described in Section 4.1.

	Placebo recipients			VRC01 recipients			All enrolled		
71	7	15	23	8	25	49	16	38	61
At least 1 event	28.0%	14.2%	9.5%	25.0%	8.8%	4.6%	13.4%	5.9%	3.7%
No events	1.5%	0.7%	0.5%	1.3%	0.4%	0.2%	0.7%	0.3%	0.2%

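### Table 4-2 gives the VRC01 safety sensitivity at n = 49, but no scenario in the SAP has more than 41 VRC01 recipients; the rate with a 90% chance of at least one SAE should be 5.5%, not 4.6%.

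*SAP*

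**What the plan says.** Section 9 of the SAP builds six sample size scenarios from three enrolment percentages (25%, 50%, 75%) and two levels of prevention efficacy in the parent trial (0% and 60%). With no efficacy, "we assume a trial size of 7, 13 or 20 placebo recipients and 14, 28, or 41 VRC01 recipients depending on the enrollment ratio". With 60% efficacy, "we assume a trial size of 8, 15, or 23 placebo recipients and an equal number of VRC01 recipients". Section 9 says of the set: "These six sample size scenarios represent estimated upper and lower bounds for sample size". Table 4-1 repeats the same six pairs of group sizes.

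Table 4-2 then expresses safety sensitivity as two true event rates for each n: the rate with a 90% chance of at least one SAE, and the rate with a 90% chance of none. The accompanying text ties the table to those scenarios ("Under the enrollment rate and PE scenarios described in protocol Section 4.1"), and the caption states how n was chosen: "Event rates are computed separately for various values of n given by the range and midpoint for the estimated number of participants among 3 groups". The printed entries are:

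| Group | n | At least 1 event | No events |
|---|---|---|---|
| Placebo | 7, 15, 23 | 28.0%, 14.2%, 9.5% | 1.5%, 0.7%, 0.5% |
| VRC01 | 8, 25, 49 | 25.0%, 8.8%, 4.6% | 1.3%, 0.4%, 0.2% |
| All enrolled | 16, 38, 61 | 13.4%, 5.9%, 3.7% | 0.7%, 0.3%, 0.2% |

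**The concern.** By the caption's rule, the largest VRC01 n should be the largest VRC01 group in any scenario. That is 41, yet the table shows 49. If the rates were also calculated at 49, the table overstates how well the study can pick up SAEs among VRC01 recipients. A reader would take from it that a 4.6% SAE rate in that group would very probably show itself at the top of the planned range, when the planned group is too small for that. Safety of the treatment interruption is primary objective 2, and Table 4-2 is the only place where the SAP says what size of safety signal it can see.

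**Working it through.** **Inputs (all from SAP section 9).**
- Criterion: 90% probability of at least one event, or of none.
- VRC01 group sizes: 14, 28, 41 (efficacy 0%) and 8, 15, 23 (efficacy 60%).
- Placebo group sizes: 7, 13, 20 and 8, 15, 23.
- Expected VRC01 infections with no efficacy: 55.

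**Step 1. Reproduce the plan's figures.** With n independent participants and a true per-participant rate p:
- at least one event with probability 0.90: 1 − (1 − p)^n = 0.90, so p = 1 − 0.10^(1/n);
- no events with probability 0.90: (1 − p)^n = 0.90, so p = 1 − 0.90^(1/n).

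| n | At least 1 event | No events | Matches Table 4-2 |
|---|---|---|---|
| 7 | 28.03% | 1.494% | yes |
| 15 | 14.23% | 0.700% | yes |
| 23 | 9.53% | 0.457% | yes |
| 8 | 25.01% | 1.308% | yes |
| 25 | 8.80% | 0.421% | yes |
| 49 | 4.59% | 0.215% | yes |
| 16 | 13.40% | 0.656% | yes |
| 38 | 5.88% | 0.277% | yes |
| 61 | 3.70% | 0.173% | yes |

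Every cell agrees to one decimal at its printed n. The formula is therefore confirmed, and the rates in the last VRC01 column really were computed at 49.

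**Step 2. Find the largest VRC01 group.** The six sizes are 8, 14, 15, 23, 28 and 41, so the range is 8 to 41. The maximum follows from its inputs: 0.75 × 55 = 41.25, taken as 41.

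**Step 3. Compare with the rest of Table 4-2.**
- All-enrolled maximum: 20 + 41 = 61, as printed. With 49 it would be 20 + 49 = 69.
- VRC01 midpoint: (8 + 41)/2 = 24.5, printed as 25. With 49 it would be (8 + 49)/2 = 28.5.
- Placebo, for comparison: range 7 to 23, midpoint (7 + 23)/2 = 15, all as printed.

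**Step 4. Recompute at n = 41.**
- At least one event: 1 − 0.10^(1/41) = 5.46%, i.e. 5.5% instead of 4.6%.
- No events: 1 − 0.90^(1/41) = 0.257%, i.e. 0.3% instead of 0.2%.

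**Step 5. What the printed rate delivers.** At p = 4.6%, the chance of at least one SAE is 1 − 0.954^41 = 85.5% with 41 participants, against 1 − 0.954^49 = 90.0% with 49.

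**The case against.** Nothing in the SAP rescues 49, but several points can fairly be made for the other side.

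- *It may be a misread digit.* The n row of the table is visibly damaged in the text version, so a 41 could have been read as 49. This fails: both printed rates in that column belong to n = 49, and n = 41 would have given 5.5% and 0.3%.
- *The scenarios are cited to protocol Section 4.1, which is not at hand.* SAP section 9 states all six scenarios itself, and Table 4-1 repeats them. The protocol is not needed to see the conflict.
- *The midpoint is weak evidence.* This stands in part. The table rounds 24.5 up to 25 but (16 + 61)/2 = 38.5 down to 38, and a maximum of 42 would give exactly 25. The midpoint rules out 49 but does not identify 41. The scenario list and the total of 61 do that.
- *The consequence is small.* This stands. The table is descriptive, and no sample size, test or planned analysis uses the cell. Primary objective 2 concerns all participants, section 10.4.1 plans no formal safety comparison between arms, and the all-enrolled columns, which bear most directly on the objective, are unaffected.
- *Correcting one column does not reconcile the whole section.* This also stands. The protocol summary in section 3 gives a sample size of 16 to 46, where 46 = 23 + 23, while Table 4-2 runs to 61. That is a separate conflict. It makes 49 no more plausible, since a VRC01 group of 49 would be larger than the whole trial as summarised there.

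**Conclusion.** The column is wrong as written. By the caption's own rule the largest VRC01 n is 41. The rate with a 90% chance of at least one SAE is then 5.5% rather than 4.6%, a difference of about 0.9 percentage points, and the rate with a 90% chance of none is 0.3% rather than 0.2%. Both errors make the study look more sensitive than it is. A true SAE rate of 4.6% does not reach the 90% criterion in any VRC01 scenario in the SAP, including the largest.

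The result assumes independent participants with a common event rate, as the table's own figures do, and takes the scenario sizes in section 9 as the intended ones. It is a modest error in a descriptive safety figure; the design and the analyses do not change.

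**What to change.** In Table 4-2, VRC01 recipients, replace n = 49 with n = 41, 4.6% with 5.5%, and 0.2% with 0.3%. Leave the VRC01 midpoint of 25 and the placebo and all-enrolled columns as they are. If the protocol carries the same table, correct it there too. The cost is one column of one table, and a stated figure that becomes slightly less favourable. When making the edit, also reconcile the 16 to 46 in section 3 with the maximum of 61 in Table 4-2, which this correction leaves open.

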### 10 STATISTICAL ANALYSIS

Analyses for primary endpoints will be performed using SAS and R. All other descriptive and inferential statistical analyses will be performed using SAS, StatXact, or R statistical software.

No formal multiple comparison adjustments will be employed for multiple safety endpoints or secondary endpoints. However, multiplicity adjustments will be made for certain laboratory assays, as discussed below, when the assay endpoint is viewed as a collection of hypotheses (eg, testing multiple peptide pools to determine a positive response).

### 10.1 Analysis variables

The analysis variables consist of baseline participant characteristics, safety, and laboratory outcomes for primary- and secondary-objective analyses.

### 10.2 Baseline comparability

Groups defined by the parent protocol treatment arms will be compared for baseline participant characteristics using descriptive statistics.

### 10.3.1 Time to ART re-initiation

The primary outcome is the time from the start of treatment interruption until the participant meets criteria to re-initiate ART.

A Cox proportional hazards model with the indicator of assignment to a mAb group versus the control group will be used to estimate the cumulative incidence in each of the infected VRC01 and infected placebo groups, as well as the hazard ratio, all with 95% confidence intervals and associated 2-sided p-values, where the model controls for baseline covariates thought to potentially predict both HIV-1 infection and the instantaneous hazard of meeting the ART reinitiation criteria. This is needed for controlling for potential postrandomization selection bias given that analyzed treatment groups are selected postrandomization. Plots of the estimated cumulative incidence will be shown by treatment group.

As a supportive analysis of this hypothesis, targeted minimum loss-based estimation (TMLE) may be used to estimate cumulative incidences of the primary efficacy endpoint over time for the pooled mAb arm and the control arm. Iterative mean-based TMLE is used for this analysis as described by Benkeser et al (2). The Super Learner (3) is used to generate initial estimates of the conditional censoring distribution and the iterated conditional means. This analysis will use TMLE as implemented in the R package survtmle available on CRAN (4).

### 10.3.2 Frequency of sustained post-treatment HIV control

The same covariate adjusted model used to estimate cumulative incidence of meeting the reinitiation criteria for ART over time, described in the previous section, will be used to compare the rates of failure to maintain HIV control at 24 weeks between the two treatment groups.

### 10.3.3 Time to viral load ≥200

Secondary endpoint 2 is time until the participant has a viral load  $\geq$  200. The same methodology used to assess time to ART re-initiation criteria will be used for this endpoint. In this analysis we will compare cumulative incidence at week 8 in each of the infected VRC01 and infected placebo groups supplemented by a sensitivity analysis based on cumulative incidence at weeks 8, 16, and 24.

### 10.4 Primary safety analysis

### **10.4.1 AE and SAEs**

AEs will be summarized using MedDRA System Organ Class and preferred terms. Tables will show by treatment arm the number and percentage of participants experiencing an AE within a System Organ Class or within preferred term category by severity or by relationship to treatment interruption. For the calculations in these tables, a participant with multiple AEs within a category will be counted once under the maximum severity or the strongest recorded causal relationship to treatment interruption. Formal statistical testing comparing arms is not planned since interpretation of differences must rely heavily upon clinical judgment.

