### 11.1 List of Tables and Listings

The following tables are included in the DSMB reports and FSR for Safety:

- Enrollment by study site
- Baseline participant characteristics
- Study status and reasons for early termination
- Visit retention, Schedule 1
- Visit retention, Schedule 2
- Visit retention, Schedule 3
- Reasons for meeting ART re-initiation criteria
- Summary of time to meeting ART re-initiation criteria
- Turnaround times for ART Re-Initiation
- SAE listing
- STI listing
- Grade 1-5 Adverse Events by System Organ Class, Ordered by Decreasing Frequency
- Grade 3+ Adverse Events by System Organ Class, High Level Term, and Severity
- Grade 1-5 Adverse Events Related to ATI by System Organ Class, High Level Term, and Severity

Additional tables include in the FSR for Safety:

- Local Lab Value Summary Statistics
- Local Laboratory Values Meeting Grade 2 AE Criteria or Above

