### 11.2 List of Figures

These graphs are included in the DSMB reports and FSR for Safety:

- Longitudinal Summaries of HIV-1 RNA Viral Load and CD4+ T-Cell Count (participant level) – all participants
- Longitudinal Summaries of HIV-1 RNA Viral Load and CD4+ T-Cell Count, restricted to participants who entered schedule 2 and to schedule 1 and 2 data points
- Cumulative Incidence of Meeting ART Re-Initiation Criteria
- Survival Plot of Time to Viral Load ≥ 200 (copies/ml)

Additional graphs included in FSR for Safety:

• Boxplots for local laboratory value (ALT, Direct Bilirubin, eGFR, Hemoglobin, Platelets, Absolute Neutrophil Count) at schedule 1 (visit 4, 8, 12, 14, 16, 18, 20, 21, 22, 23, 25, 27), schedule 2 (visit 40, 44, 48, 50, 52, 54, 56, 58, 60, 62, 64, 66), and schedule 3 (82, 84, 86, 89, 91)

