# Appendix I: Schema

SCHEDULE 3	FOLLOW UP FOLLOW UP ON ART ON ART WEEKS 12-28 WEEKS 40-52	Q4 WEEKS Q12 WEEKS	Q8 WEEKS Q12 WEEKS	Q12 WEEKS Q12 WEEKS
S	FOLLOW UP ON ART WEEKS 0-12	Q2 WEEKS	Q4 WEEKS	Q4 WEEKS
	PRE- REINITIATE ART	>	>	ı
	ATI + Viremia WEEKS 40-52 	Q4 WEEKS	QB WEEKS	QB WEEKS
SCHEDULE 2	ATI+Viremia WEEKS 10-36	Q2 WEEKS 	Q4 WEEKS*	EEKS
	ATI+Viremia WEEKS 0-8	WEEKLY	Q2 WEEKS	Q4 WEEKS
	ATI WEEKS 28-52 	Q4 WEEKS	Q8 WEEKS	Q8 WEEKS
CHEDULE 1	ATI WEEKS 10-24	Q2 WEEKS	Q4 WEEKS	EEKS
S	ATI WEEKS 0-8	WEEKLY	Q2 WEEKS	W #5
Ī	PRE. DISCONTINUE ART	N	٨	*
	SCREEN	٨	>	٨
		Plasma HIV RNA	CD4+& CD8+ T cell counts	Hematology & Chemistries

. QUARTERLY FOLLOW-UP VISITS MAY CONTINUE BEYOND WEEK 5.2 FOR PARTICIPANTS WHO DO NOT MEET CRITERIA FOR TRANSITION TO SCHEDULE 2.

Page 14 of 14

 QUARTERLY FOLLOW-UP VISITS MAY CONTINUE BEYOND WEEK 5.2 FOR PARTICIPANTS WHO DO NOT MEET CRITERIA FOR ART RE-INITIATION.
3 OR WEEKLY FOR WEEKS 10-24, IF VL ≥ 200 copies/ml.

OR Q2 WEEKS FOR WEEKS 10-24 IF VL ≥ 200 copies/mL

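### Minor: the AE tables do not separate events with onset during ATI from events after ART restart, although the safety objective concerns ATI

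*SAP*

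**What the plan says.** Section 9 of the SAP (sample size considerations for safety) gives the purpose: "The goal of the safety evaluation for this study is to identify safety concerns associated with ATI". Primary objective 2 in Section 5 is likewise the safety of ATI.

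Section 10.4.1 sets the summary measure: "Tables will show by treatment arm the number and percentage of participants experiencing an AE within a System Organ Class", continuing "or within preferred term category by severity or by relationship to treatment interruption". The counting rule is that "a participant with multiple AEs within a category will be counted once under the maximum severity or the strongest recorded causal relationship" to treatment interruption. No between-arm test of AEs is planned.

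Section 11.1 lists three AE tables: "Grade 1-5 Adverse Events by System Organ Class, Ordered by Decreasing Frequency", a Grade 3+ table, and a table of ATI-related events. None names an onset period or a time at risk.

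Appendix I continues follow-up after ART restart. Schedule 3 begins with "FOLLOW UP ON ART WEEKS 0-12" and is drawn to week 52. Elsewhere the SAP does use period structure: one viral load and CD4 figure in Section 11.2 is "restricted to participants who entered schedule 2 and to schedule 1 and 2 data points", the laboratory boxplots are listed by schedule, and visit retention is tabulated by schedule.

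**The concern.** A participant can spend longer on ART in Schedule 3 than off ART in Schedules 1 and 2. If AEs from both periods enter one percentage, a table meant to describe ATI may largely describe follow-up on ART. A real rise in AEs off ART would then be diluted. The ATI-related table does not settle this, because it sorts events by a causality judgement and not by when they began. Time to criteria, turnaround to ART, retention and ATI discontinuation are all reported, but none is linked to the AE counts.

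What is at stake is how descriptive tables are read by the DSMB and in the final report. No inference depends on it.

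**Working it through.** **Inputs from the SAP (Section 9, time to re-initiation criteria).** Weibull survival with λ = exp(-2.932) = 0.0533 per week and p = 2.014; exponential censoring at 20% per year, so c = -ln(0.8)/52 per week; maximum 72 weeks. The schema draws Schedule 3 to week 52, with an intermediate stage ending at week 28.

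**Assumed, because the SAP gives no figure.** A constant AE rate of 0.5 to 2 per person-year on ATI, with 1 as the reference; a rate on ART equal to that or half of it; 28 or 52 weeks on ART for those who meet the criteria; AEs collected throughout Schedule 3.

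**1. The plan's own figures.** Median = (ln 2)^(1/p)/λ = 15.64 weeks (stated 15.6). HR^(-1/p) for HR 0.6, 0.5, 0.4, 0.3 gives increases of 28.9, 41.1, 57.6 and 81.8%, which agrees with "These hazard reductions correspond to 29%, 41%, 58%, and 82% increases in the median time to meet re-initiation criteria". Simulated log-rank power at HR 0.4 and 50% enrolment is 72.5% and 61.6% (stated 72% and 62%). The model is reproduced.

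**2. Time on ATI, no VRC01 effect.** The mean is the integral from 0 to 72 of exp(-(λt)^p)·exp(-ct), which is 15.9 weeks. The probability of meeting the criteria is 0.932.

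**3. Mixing at 1 AE per person-year in both periods, no VRC01 effect.** Integrating exp(-t/52) over the same model, 0.690 of participants have no AE on ATI and go on to meet the criteria, and 0.057 have no AE on ATI and are censored.
- AE on ATI: 1 - 0.690 - 0.057 = 0.25.
- AE at any time with 52 weeks on ART: 1 - 0.057 - 0.690·exp(-1) = 0.69.
- Share of those counted with no AE on ATI: (0.690 - 0.254)/0.690 = 0.63. (Here the first 0.690 is the pooled share, which happens to equal the probability above.)

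Over the assumed ranges this share runs from 0.34 (2 per person-year on ATI, 1 on ART, 28 weeks) to 0.69 (0.5 throughout, 52 weeks).

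**4. Dilution of a true signal.** The ATI rate doubles from 1 to 2 per person-year; the ART rate stays at 1.

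| Table | ATI rate 1 | ATI rate 2 | Change (points) |
|---|---|---|---|
| Onset on ATI | 25% | 43% | 18 |
| Pooled, 28 weeks on ART | 54% | 65% | 11 |
| Pooled, 52 weeks on ART | 69% | 76% | 7 |

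**5. Arm imbalance, only if VRC01 works.** At HR 0.6, 0.5, 0.4 and 0.3, mean time on ATI is 20.2, 22.0, 24.4 and 27.8 weeks, or 27, 39, 54 and 75% longer than 15.9. Take 1 AE per person-year in both arms and the six size scenarios of Section 9.
- Pooled table: at 52 weeks on ART for those who meet the criteria, 69% v 70-72%, or 0.05-0.24 standard errors. Across 28 or 52 weeks, given to those who meet the criteria or to everyone, the gap is about 1-8 points and at most 0.59 standard errors.
- ATI-only n (%) table: 25% v 31-39%, or 0.24-1.10 standard errors, above 1 in 1 of 24 cells.

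**The case against.** The strongest reply is that nothing here is misstated. Participant-level n (%) with no testing is a coherent descriptive plan for a small study, and late consequences of an interruption may appear after restart, so a whole-study table is a defensible view. This stands, and it is why the whole-study tables should be kept and the point is minor.

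Second, the SAP gives no AE collection window for Schedule 3. A reader might infer that AEs on ART are certainly pooled. The document does not support that: if the protocol restricts AE collection on ART, the mixing shrinks or disappears.

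Third, much is already planned: breakdowns by severity and relationship, an ATI-related table, SAE and STI listings, and laboratory grades by timepoint after ATI start. It would be wrong to say that the SAP offers nothing specific to ATI. What remains missing is separation of AEs by onset.

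Fourth, a reader might infer that longer time off ART on VRC01 would seriously distort the planned comparison by arm. The numbers do not support this. The gap in the pooled table is at most 0.59 standard errors under the reference rate, and there is none without a VRC01 effect. The larger gap belongs to an ATI-only table, which the SAP does not plan. It does show that an onset split needs time at risk beside it.

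Finally, first-event rates are no cure. If AEs occur only in the first 8 weeks of ATI, n (%) is nearly unbiased (25% v 25-26%), while the first-event rate ratio would be 0.81 to 0.61 with no true difference.

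**Conclusion.** The point holds as a minor, inexpensive improvement. The AE tables, as specified, separate ATI events only by attribution, although the objective is the safety of ATI. The size is conditional on AE collection through Schedule 3 and on assumed constant AE rates. The model also ends ATI at the criteria, so actual time off ART would be somewhat longer. Under those conditions about a third to two thirds of participants counted with an AE would have none on ATI, and an 18-point rise on ATI would show as 7 to 11 points in the pooled table. Arm imbalance does not carry the point, and no test or decision rule in the SAP is affected.

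**What to change.** In Section 10.4.1 and the Section 11.1 AE tables:

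- Keep the whole-study n (%) tables as planned.
- For overall, Grade 3+ and ATI-related AEs only, not for every System Organ Class or preferred term, add n (%) by onset period: ATI up to ART restart, and on ART. Show this by arm and pooled, with participant-weeks at risk in each period.
- State in the SAP, or by reference to the protocol, the period over which AEs enter these tables.
- Optionally show cumulative incidence of first AE by week since ATI start, in preference to first-event rates.

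The cost is SAP wording, a period split and a time-at-risk row, built from dates that the time-to-criteria and turnaround tables already need. The downside is larger tables and sparse cells. For example, at 15 v 15 participants, 1 AE per person-year and a 60% hazard reduction, about 4 v 5 participants would have a first AE on ATI.
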